8.3. Planned Analysis and Data Summaries

8.3.1. General Analysis Techniques

In general, continuous variables will be summarized by providing the number of subjects with available data (n), the mean, median, standard deviation, minimum, and maximum values. For categorical variables, the number and percentage of subjects that are in each category will be provided. Unless otherwise specified, the denominator for percentages will be all relevant subjects in a particular analysis, including those for whom data are not available, i.e., “not reported” or “not available” will generally be considered a separate

category and included in the displays of data, with the denominator for percentages including these subjects. Subjects will be summarized by their assigned and actual treatment group (e.g., ciNPT and SOC).

8.3.2. Subject Disposition

Summaries of disposition will be tabulated by treatment group. The number and percentage of subjects in each analysis set will be described, as will the number (and percentage, if relevant) of subjects who:

- provided informed consent;
- failed screening, and reason for failing screening;
- were randomized;
- were randomized and treated;
- discontinued early from the study for any reason, along with the reason for discontinuation (if the reason is adverse event, the system organ class and preferred term); and
- completed the study as planned.

Subject disposition also will be described in a flowchart (CONSORT diagram²²).

8.3.3. Demographic and Baseline Characteristics

Demographic characteristics (age, sex, race, and ethnicity), baseline characteristics, and other disease characteristics, will be summarized according to the general techniques in section 8.3.1. Subjects in the Safety, ITT, mITT, Per-Protocol, and/or mPP Analysis Sets will be summarized within each treatment group and overall.

8.3.4. Analysis of Primary Endpoint

The analyses described in this section will be performed for the overall primary endpoint, “Any Surgical Site Complication (SSC)”, within 90 days of TKA revision, and repeated for each type of complication.

The proportion of subjects with each possible result – “Occurred”, “No occurrences”, or “Incomplete follow-up” will be reported, using the mITT Analysis Set as the denominator. See section 8.1.1 for definitions of these outcomes.

The comparative analysis of the primary endpoint will only consider subjects in the mITT Analysis Set, i.e., subjects with “Incomplete Follow-up” will be excluded. The proportions

of subjects with “Occurred” will be calculated within each treatment group and compared between treatment arms using a Cochran-Mantel-Haenszel (CMH) p-value stratified for type of revision (aseptic vs. septic). The difference between the proportions (ciNPT – SOC) and asymptotic 95% confidence interval will be computed. At the final analysis, a two-sided significance level adjusted for the interim efficacy analyses and potential sample size recalculation (e.g., $\alpha = 0.048$ if interim look is at $t=0.50$ and no sample size adjustment is made) will be used to compare the SSC proportions between the two treatment arms.

Supportive/exploratory analyses of the primary efficacy endpoint, SSC, may include:

- analyses comparing the treatment groups for the septic and aseptic revisions;
- analyses comparing the treatment groups for age, BMI, race/ethnicity, material used in the revision, and sex subgroups;
- analyses comparing the heterogeneity of the treatment groups across clinical sites;
- multivariable analyses comparing the treatment groups with covariate adjustment where possible covariates might include (but not limited to) age, BMI, sex, type of revision (aseptic or septic), and subject co-morbidities;
- Fisher’s exact test presenting the unstratified p-value;
- A repeat of any analysis above using the Per-Protocol and/or mPP Analysis Sets;

and other exploratory analyses as deemed appropriate.

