8. STATISTICAL CONSIDERATIONS

8.1. Endpoint Definitions for Analysis

8.1.1. Primary Endpoint – Subject Incidence SSC

The primary endpoint is the incidence of surgical site complications (SSCs) within 90 days of TKA revision in subjects treated with ciNPT as compared to standard of care surgical dressing. The SSC endpoint includes any occurrence of superficial SSI, deep SSI, dehiscence, seroma, hematoma, skin necrosis, or continued drainage as outlined in section 4.11.1. For this endpoint there are three possible outcomes:

- “Occurred”, which is assigned if the subject had one or more occurrences of any complication and the onset date of the complication was between the time of the TKA revision and not later than 90 days after;
- “No occurrences”, which is assigned if the subject had no known occurrences of a complication within 90 days of the TKA revision and was assessed at least once on or after the 90th day following the TKA revision;
- “Incomplete follow-up”, which is assigned if the subject had no occurrences of the complication within 90 days of the TKA revision and did not have an assessment at least 90 days after the date of the revision surgery.

If a subject experiences one occurrence of any of the six complications, the primary outcome will be considered “Occurred”.

For each component of the SSC, the start date of the complication will be recorded in order to calculate the number of days from the revision surgery until occurrence of the event. If the complication did not occur, the number of days will be calculated using the last assessment which confirmed the subject to be complication-free.

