8.2. Analysis Sets

The following analysis sets will be used:

- ITT Analysis Set – The ITT (intention-to-treat) Analysis Set will consist of all randomized subjects. Subjects will be analyzed according to the treatment allocated at randomization.
- Safety Analysis Set – The Safety Analysis Set will consist of all randomized subjects who received any study-related treatment procedures. It is expected that all randomized subjects will be treated. All safety results will be presented based on the Safety Analysis Set. Subjects will be analyzed according to the study treatment they received immediately following the TKA revision.
- Modified ITT (mITT) Analysis Set – This set will include subjects in the ITT Analysis Set with the following: 1) an SSC on or before 90 days post-TKA revision or 2) no known occurrence of an SSC within 90 days of the TKA revision and was assessed at least once on or after the 90th day following the TKA revision. Subjects will be analyzed according to their randomized treatment assignment.
- Per-Protocol Analysis Set – This will include subjects in the mITT Analysis Set and had no disqualifying protocol deviation(s) that would impact the interpretation of the primary endpoint. The disqualifying protocol deviation(s) for exclusion from this set will be defined and documented in a blinded fashion prior to the final database lock by the Protocol Deviation Review Committee. Subjects will be analyzed according to their randomized treatment assignment.
- Modified Per-Protocol (mPP) Analysis Set – This will include subjects in the Per-Protocol Analysis Set excluding any subjects that received prohibited therapy as described in section 4.15 or any subjects that received alternative therapy following the study treatment period.

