8.4.2. Sample Size Determination

The primary endpoint of this study is the subject incidence of SSC as defined in section 4.11.1. The incidence rates of SSC are different for septic and aseptic revisions; the assumed SSC rate is 33% for septic and 6.9% for aseptic. This study plans to enroll at least 50% septic revisions overall. These enrollment rates lead to an assumed pooled SSC rate of 20% in the SOC dressing arm.

Assuming an overall type 1 error rate of 0.05, with a two-sided hypothesis test, the study will have at least 80% power to detect a difference of 10% (50% reduction) in SSCs in the ciNPT arm with 199 subjects in each treatment arm, with one interim analysis at about 50% of the evaluable subjects for a total of 398 subjects using the likelihood ratio test. With an estimated 5%-10% loss, a non-binding interim analysis for superiority at approximately 50% of the evaluable subjects using O'Brien-Fleming method for monitoring boundaries, the planned sample size will be inflated for potential loss of follow-up for a total of 440 subjects.

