5 ANALYSIS SETS

The following analysis sets are planned for this study:

- Safety Analysis Set: The Safety Analysis Set consists of all randomized subjects who received any study-related treatment procedures. Subjects will be analyzed according to the study treatment they received immediately following the TKA revision.
- ITT Analysis Set: The ITT (intention-to-treat) Analysis Set consists of all randomized subjects. Subjects will be analyzed according to their randomized treatment assignment.
- mITT Analysis Set: The modified ITT Analysis Set will include subjects in the ITT analysis set with the following: 1) who had any SSC on or before 90 days post TKA revision, or 2) had an assessment of SSC on or after 90 days post TKA revision and had no known occurrence of any SSC within 90 days post the TKA revision. Subjects will be analyzed according to their randomized treatment assignment.
- Per-Protocol Analysis Set: This will include subjects in the mITT analysis set who had no disqualifying protocol deviation(s) that would impact the interpretation of the primary endpoint. The disqualifying protocol deviation(s) for exclusion from this set will be defined and documented in a treatment-blinded fashion prior to the final database lock by the Protocol Deviation Review Committee. Subjects will be analyzed according to their randomized treatment assignment.
- Modified Per-Protocol (mPP) Analysis Set: This will include subjects in the Per-Protocol analysis set excluding any subjects who received prohibited therapy as described in Section 4.15 of the study protocol or any subjects that received alternative therapy following the study treatment period.

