8.5 Primary Endpoint Analysis

The proportion of subjects with each value of “Occurred” or “No occurrences” or “Incomplete-Follow-up” will be summarized, as applicable, by treatment arm based on the ITT, mITT, Per Protocol and Modified Per Protocol analysis sets.

Superiority Testing

The following hypothesis will be tested for superiority:

$$\text{Null } H_0: \Delta_{\text{ciNPT-SOC}} = 0$$

$$\text{Alternative } H_a: \Delta_{\text{ciNPT-SOC}} \neq 0$$

where $\Delta_{\text{ciNPT-SOC}}$ is the difference in the proportion of subjects in the ciNPT arm with at least one SSC and the proportion of subjects in the SOC dressing arm with at least one SSC.

There are three populations including subpopulations: septic, aseptic and combined (septic + aseptic).

i) For the combined population, a Cochran-Mantel-Haenszel (CMH) test stratified by randomized type of revision (Septic, Aseptic) will be used to compare the SSC incidence rates between two treatment arms based on the mITT analysis set. The odds ratio and its asymptotic 95% confidence interval will be computed. This test is equivalent to the test of difference for the proportions. ii) For the septic and aseptic subpopulations, a Chi-square or Fisher's test, as appropriate will be performed within each randomized revision type for SSC incidence rates between treatment groups based on the corresponding mITT analysis set.

At the final analysis, a two-sided significance level of $\alpha = 0.048$ will be used to compare the SSC proportions between the two treatment arms after adjustment for the interim analysis.

Based on the interim analysis results, we will be considering three possible cases:

- Case 1: population was not enriched at interim analysis;
- Case 2: population was enriched by septic at interim analysis;
- Case 3: population was enriched by aseptic at interim analysis.

If the population is not enriched, then analyses described in Case 1 will be carried out. If the population is enriched, then analyses described in Case 2 or Case 3 will be carried out. If the population is enriched by increasing enrollment of one of the subpopulations based on statistical information, a closed testing strategy to ensure a strong control of type-1 error for the primary endpoint will be carried out based on two tests for the primary analysis.

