8.7.6 Time to SSC Analysis

Time to SSC: defined as the time in day(s) from the date of TKA revision to the first SSC event and is calculated as:

$TTSSC = (\text{Start Date of the first SSC} - \text{Date of the TKA revision}) + 1$

Censoring will occur for the following:

- 1.) Subjects who experience their first SSC on the day of TKA revision after initial dressing application will be considered to have a time to SSC of 1 day.
- 2.) Subjects, who do not have any SSC assessment after initial dressing application and they withdraw before the first scheduled SSC assessment at the end of treatment, will be censored at the date of TKA revision.
- 3.) Subjects who do not have any SSC assessment at Day 90 will be censored at Day 90 or end of study date, whichever comes first.

A Kaplan-Meier curve will be generated for each treatment arm and the quartile estimates will be generated as well. A log-rank test will be used to compare the time-to-SSC between treatment arms. These analyses may be repeated utilizing data calculated from the additional way of calculation described above.

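### The mITT rule modestly overstates the SSC rates and the ciNPT − SOC risk difference under ordinary equal loss, and no corrected day-90 estimate is pre-specified

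*Protocol*

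**What the plan says.** - **Analysis set.** Protocol 8.3.4: "The comparative analysis of the primary endpoint will only consider subjects in the mITT Analysis Set". SAP 8.5 also runs the combined-population CMH test on mITT.
- **Who is kept.** Protocol 8.2 admits a randomized subject with "an SSC on or before 90 days post-TKA revision" and sets no follow-up requirement. An SSC-free subject is admitted only if he or she "was assessed at least once on or after the 90th day following the TKA revision". SAP section 5 has the same two limbs; the first reads "who had any SSC on or before 90 days post TKA revision".
- **Who is dropped.** Protocol 8.1.1 classes as incomplete follow-up an SSC-free subject who "did not have an assessment at least 90 days after the date of the revision surgery".
- **Effect measure.** Protocol 8.3.4 reports the ciNPT − SOC difference in proportions. SAP 8.5 reports an odds ratio and keeps the hypothesis on the difference; SAP section 10 records the change.
- **Missing data.** SAP 7.3 provides no imputation for the primary endpoint.
- **Use of partial follow-up.** Only SAP 8.7.6 censors: "A Kaplan-Meier curve will be generated for each treatment arm". It is exploratory and unstratified, and gives no day-90 difference. It censors subjects lacking a day-90 assessment at the earlier of day 90 and the end-of-study date. Protocol 8.1.1 instead counts time to the last complication-free assessment.
- **Expected loss.** Protocol 8.4.2 and SAP 2.1 plan for 5%-10%.

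**The concern.** Membership of the analysis set depends on the outcome. A subject with an SSC on day 2 who is lost on day 3 counts in full. A subject last seen SSC-free on day 60 disappears from the denominator. Each arm's proportion is events / (events + completed non-events), which exceeds the 90-day risk whenever some losses occur after SSCs have begun. No informative withdrawal is needed.

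At stake are the SSC rates readers will quote and the absolute benefit, which errs in favour of ciNPT if ciNPT works.

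If loss differs by arm, the odds ratio and the test are affected too. That is possible: the trial is open-label, and Protocol 4.15 withdraws subjects who cross over after study treatment without an SSC, after which Protocol 4.4.2 ends data collection. Protocol 3.2 says all subjects are followed for 90 days whatever treatment they receive. These passages need to be reconciled.

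**Working it through.** **1. The plan's own figures.** Protocol 8.4.2 gives SSC rates of 33% (septic) and 6.9% (aseptic), at least half septic, a 50% reduction and 80% power: "Assuming an overall type 1 error rate of 0.05, with a two-sided hypothesis test".
- Pooled SOC rate: 0.5 × 33% + 0.5 × 6.9% = 19.95%, stated as 20%.
- Per arm, 20% v 10%: [1.96 √(2 × 0.15 × 0.85) + 0.8416 √(0.2 × 0.8 + 0.1 × 0.9)]² / 0.10² = 1.4106² / 0.01 = 199. This matches.
- Two-look power at 199 per arm with levels 0.0052 and 0.048 is 79.5% (pooled variance) to 80.3% (unpooled).
- 1 − 398/440 = 9.5%, so 440 randomized allows for loss near the top of the planned range.

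**2. Expected mITT rate.** Let p be the true 90-day risk, d the loss (random), and k the share of lost subjects' SSCs that occur, and are recorded, before loss. The documents do not give k, so the full range 0 to 1 is shown.

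mITT rate = p[(1−d) + dk] / {p[(1−d) + dk] + (1−p)(1−d)}

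For d = 0.10 and k = 1: SOC 0.20 / (0.20 + 0.72) = 0.2174; ciNPT 0.10 / (0.10 + 0.81) = 0.1099.

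| Loss, both arms | k | SOC (true 20%) | ciNPT (true 10%) | Difference (true 10), points |
|---|---|---|---|---|
| 5% | 0 | 20.0% | 10.0% | 10.0 |
| 5% | 0.5 | 20.4% | 10.2% | 10.2 |
| 5% | 1 | 20.8% | 10.5% | 10.4 |
| 10% | 0 | 20.0% | 10.0% | 10.0 |
| 10% | 0.5 | 20.9% | 10.5% | 10.4 |
| 10% | 1 | 21.7% | 11.0% | 10.75 |

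The overstatement of the difference at k = 1 is 3.6% (5% loss) and 7.5% (10% loss) in relative terms. k = 0.5 corresponds to SSC onset and loss both uniform over 90 days; earlier onset moves k towards 1.

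**3. Odds ratio.** The mITT odds are [p/(1−p)] × [1 + dk/(1−d)]. If d and k are the same in both arms, the second factor cancels: (0.10/0.90) / (0.20/0.80) = 0.444 in every row.

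**4. Simulation** (440 subjects, two equal strata, planning rates, stratified CMH at 0.048 without the interim look, 20,000 runs, equal loss of 5% or 10%).
- Under the null the test rejects in 4.5% to 4.9% of runs, against 4.8% nominal.
- Under the alternative power is 84.5% to 86.3%, against 86.4% to 86.8% with full follow-up, so the rule does not raise power.
- Day-90 Kaplan-Meier on the same data (3,000 runs) recovers 19.9%-20.0% v 9.9%-10.0%.

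**5. Unequal loss inside the planned range.** With no true effect at a 20% rate and k = 1, loss of 5% v 10% gives 20.8% v 21.7%, a spurious 0.9 points. With the true 20% v 10%, SOC loss of 10% and ciNPT loss of 5% give a difference of 11.3 points and an odds ratio of 0.421; the reverse gives 9.8 points and 0.469.

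**The case against.** The strongest case against is that the final SAP has moved away from the biased measure. SAP 8.5 reports an odds ratio, which step 3 shows is unbiased under equal random loss with similar SSC timing. That stands. The bias is confined to the arm proportions, which are still reported, and to the risk difference of Protocol 8.3.4, on which the hypothesis is still written.

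It is also small. The standard error of the difference at 199 per arm is √(0.25/199) = 3.5 points, so the worst case of 0.75 is about 0.2 standard errors. If SSCs are captured only at scheduled visits (assumed days 7 and 37 before day 90), 10% loss gives a difference of 10.2 to 10.5 points; unscheduled visits would raise this.

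The plan has partial safeguards. SAP 8.5 tabulates incomplete follow-up by arm on ITT, so loss will be visible. SAP 8.5.1 lists an ITT CMH test among analyses that may be performed, but does not say how incomplete follow-up is coded. If those subjects are dropped, it repeats mITT. If they count as non-events, the expected rate is p[(1−d) + dk]; at d = 10% and k = 0.5 that is 19.0% v 9.5%, a difference of 9.5. Neither coding gives a corrected estimate.

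Two stronger readings are tempting. A reader might infer that the final test, for which SAP 8.5 says "a two-sided significance level of $\alpha = 0.048$ will be used", exceeds its level. Under equal loss it does not. At an assumed 15% v 5% loss, simulated rejection was 5.2%-6.3%, but 15% lies outside the planned range and nothing in the documents supports such a gap; at 10% v 5% it stays close to 5%. A reader might also blame the day-90 visit window for having no minus tolerance. Entry is not tied to that window: any assessment on or after day 90 qualifies.

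**Conclusion.** The concern holds as a modest estimation bias. At 5%-10% random, equal loss, the SOC rate is overstated by up to 0.8-1.7 points, the ciNPT rate by up to 0.5-1.0, and the risk difference by up to about 0.4-0.75 points on 10, roughly half that with uniform onset and loss. These sizes rest on the planning rates and on assumed timing. The odds ratio and the test level are safe provided loss and SSC timing are similar in both arms. If loss differs by arm they are affected; the open-label design and the Protocol 4.15 withdrawals make that possible, but the documents give no basis for expecting a particular size. This warrants a supportive estimate, not a new primary test.

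**What to change.** Keep the stratified CMH test on mITT as the confirmatory test, so the alpha plan is untouched. In SAP 8.5, before database lock, add a named supportive estimate:

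- **Population:** all randomized subjects (ITT), by randomized arm and randomized revision type.
- **Estimate:** Kaplan-Meier SSC risk at 90 days after revision, R, in each arm within the septic and aseptic strata. SAP 8.7.6 adds one day to its time variable, so the cut-off must be stated on a consistent scale.
- **Combination:** Σ wₛ (R_ciNPT,s − R_SOC,s), where wₛ is stratum s's share of all randomized subjects, with a 95% CI from the Greenwood variances weighted by wₛ². Report the weighted risk per arm as well.
- **Censoring:** SSC-free subjects at their last SSC assessment, or at 90 days if assessed on or after that day, in line with Protocol 8.1.1. Align SAP 8.7.6 to this rule.
- **Reporting:** beside the mITT proportions and odds ratio, with no added significance condition.

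If the ITT CMH test in SAP 8.5.1 is kept, state how incomplete follow-up is coded.

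The cost is SAP wording, one extra table and some new programming, since the planned Kaplan-Meier analysis is unstratified and censors differently. The reported benefit will probably be slightly smaller. The estimate assumes non-informative censoring, which the Protocol 4.15 withdrawals (repeat surgery on the incision, re-revision, SSC-free cross-over) may strain; reasons for censoring should be tabulated by arm.

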8.3.5. Analysis of Secondary Endpoints

Any SSI (superficial or deep) and Deep SSI will be analyzed in a similar fashion as the primary endpoint described in section 8.3.4. Superficial and Deep SSI will be analyzed separately and jointly; individual infection components will be summarized descriptively.

8.3.6. Exploratory Endpoints

In general, analyses will be performed on subjects in the ITT and/or mPP Analysis Sets using methods outlined in section 8.3.1. The number of subjects in each treatment arm at each scheduled visit with adequate assessments will be summarized for each visit. Assessments performed outside the scheduled visit windows may not be included in the models but will be listed separately. The patterns of missing data will be presented using

descriptive analyses. Other statistical analyses exploring the effects of imputation methods for non-response may be generated as appropriate.

Because the analyses are exploratory, no adjustment will be made for multiple comparisons. Confidence intervals may not be created for subsets with less than ten subjects, although standard errors or deviations will be presented to provide a measure of variability. Complete details for all endpoints will be outlined in the Statistical Analysis Plan.

